3.1.3 Trial Schedule

Estimated First Patient First Visit:	Q4 2019
Estimated Last Patient First Visit:	Q2 2023
Estimated Last Patient Last Visit/End-of-Trial:	Q2 2023
Post-trial activities completed:	Q2 2025

3.2 Planned Number of Trial Centers and Subjects

Approximately 100 maternal subjects will be randomized at approximately 15 trial centers in the United States. It is anticipated that approximately 250 maternal subjects will be screened. See Section 9.1.

3.3 Interim Analysis

An unblinded interim analysis for futility assessment is planned when approximately 50% of the planned 100 subjects have completed the assigned treatment period of the trial. The interim analysis

will assess the futility of merotocin compared to placebo (see Section 9.9).

3.4 Data Monitoring Committee

An independent Data Monitoring Committee (DMC) consisting of medical and biostatistics experts will be established to review the interim clinical data for the futility assessment (see Section 9.9). The DMC have access to the unblinded interim data and will make a recommendation regarding the continuation of the trial. The responsibilities, membership, and procedure for the futility assessment, the measures used to protect the blind, the integrity of the trial, and the communication pathway to the Sponsor are specified in the DMC charter.

3.5 Safety Committee

A Safety Committee will be established by the Ferring Global Pharmacovigilance Department (GPV) and will consist of at least Ferring's pharmacovigilance physician, Ferring's global regulatory affairs representative, the trial statistician, the medical monitor and an external neonatology specialist as specified in the Safety Committee charter.

The Safety Committee will meet regularly, at least every third month, to evaluate the safety of the subjects in terms of AEs, safety laboratory parameters, results from milk composition analyses, and any concentration of merotocin in milk on an ongoing basis. In case of any safety concerns, the Safety Committee can recommend whether the trial should be stopped or should continue with or without modifications to ensure the safety of the subjects and to maintain an appropriate benefit/risk ratio for the subjects participating in the trial.

The Safety Committee will not routinely unblind data on the individual level but may decide to unblind data on the group level to allow further analysis. If unblinding on the individual treatment level is required, an ad hoc safety group consisting of an independent GPV representative, an independent statistician and an external neonatology expert other than the expert in the Safety Committee will be formed to analyze the unblinded data. None of the ad hoc safety group members will be involved in the conduct of the trial.

The analyses of merotocin concentrations in milk will be performed by the Bioanalysis Department on an ongoing basis throughout the trial. Any quantifiable amount of merotocin observed in any of the samples will be communicated to the Safety Committee in a blinded manner. If one or more milk samples with quantifiable amount of merotocin is reported, the treatment allocation will be unblinded on the individual level by an ad hoc safety group, consisting of an independent GPV representative, an independent statistician and an external neonatology expert other than the expert in the Safety Committee. The ad hoc safety group will also review unblinded safety data. The United States Food and Drug Administration (FDA) will be notified of the finding and will be provided with observed neonatal AEs.

A Safety Committee charter will specify the relevant details and responsibilities of the Committee.

3.6 Discussion of Overall Trial Design and Choice of Control Groups

3.6.1 Trial Design

This trial will investigate the efficacy and safety of repeated intra-nasal administrations of merotocin compared to placebo in increasing milk production in women with preterm delivery and inadequate initial milk production.

The trial design employs best practices for establishing an adequate milk supply. All maternal subjects will institute a high frequency milk expression regimen and will receive standardized lactation counselling and ongoing support consistent with guidelines for promoting lactation in this population.

There is no approved product for women with lactation deficiency in the country where the trial will be conducted. Some pharmacologic agents are used in clinical practice to increase milk supply, but there is only limited medical evidence to support the safety and efficacy of the use of these agents to correct lactation deficiency in women with preterm delivery.^{25,26,27} For these reasons, a placebo comparator is necessary to evaluate the potential of merotocin to increase milk production in this population.

The window for randomization, originally set to 96 to 144 hours of delivery, was chosen to enhance the probability of selecting maternal subjects who truly have an inadequate milk supply but also to ensure that intervention is instituted early enough in the postpartum period to have an impact. By the amendment (dated 06-04-2022), the window was expanded to 96 to 192 (+4) hours of delivery to allow adequate time for the maternal subjects to appreciate and understand the value of participating in the trial, with a negligible risk for any negative impact on induction of lactation. Allowing randomization earlier in the postpartum period might select maternal subjects, whose milk supply appears inadequate due to delayed onset of lactogenesis II but who may ultimately establish an adequate milk supply without intervention.

The treatment period of 14 days was primarily chosen because, if merotocin is effective, it would act early in the process of establishing lactation by promoting full emptying of the breast via milk ejection and possibly by increasing prolactin levels to increase milk synthesis. Both of these are important to establish an adequate milk supply. The duration of treatment needed for merotocin to achieve its potential effect in increasing milk production is not known. A treatment duration of 14 days will allow for exploration of when the treatment effect of merotocin begins and how the effect may develop over time.

To obtain the required number of maternal subjects within the scheduled recruitment period and to produce generalizable results, a multicenter design has been chosen. Maternal subjects will be randomly assigned to their treatments, and both the maternal subjects and investigators will be

blinded to the assignment to reduce bias.

3.6.2 Selection of Endpoints

The primary endpoint for this trial is volume of MoM produced over Days 1 to 14. The volume of MoM produced for each treatment day will be recorded and derived for each subject. These daily volumes of MoM produced will be analyzed using a repeated measures analysis of covariance (ANCOVA) to allow for investigation of the overall treatment effect in the primary analysis and the onset of treatment effect of merotocin compared to placebo in supportive analyses.

The secondary endpoints (Section 2.2) will provide further evaluation of the milk volume produced over Days 1 to 14. The recommendation for a lactating mother of a non-nursing preterm infant is to establish an adequate milk supply, defined as a daily milk volume of ≥ 500 mL, during the first two weeks after delivery. Evidence suggested that adequate milk production at 1-2 weeks postpartum, particularly 1 week postpartum, is highly predictive of milk adequacy at 6 weeks postpartum.¹ Therefore it is clinically relevant to assess the time it takes for maternal subjects to reach the target daily milk volume of ≥ 500 mL or a more ambitious goal of ≥ 750 mL. Striving for reaching these targets sooner than later may also motivate mothers to continue milk expression on a regular basis. For the same purpose, an additional secondary endpoint, an assessment of the proportion of women with an ‘adequate milk supply’ over Days 1 to 14 is also included.

The secondary endpoints will also examine whether any observed treatment effect of merotocin is maintained over the three days after discontinuation of treatment. The infant body weight is a standard growth parameter to indicate that the infant is growing and developing as expected. The safety assessments selected are standard for the maternal subjects.

The effect of merotocin on milk composition as well as the relationship between merotocin exposure and milk volume will be explored.

For the post-trial endpoint related to time to tolerance of full enteral feed, 150 mL/kg/day is used to define full enteral feed in order to standardize the assessment.^{28,29} For the long-term follow-up of infants, the administration of ASQ-3 has been recommended by both FDA and American Academy of Pediatrics to screen child developmental disorders.

3.6.3 Blinding

The present trial is double-blind. Investigators, trial center staff and maternal subjects will remain blinded to treatment allocation until the database has been locked and the trial has been unblinded. Blinding is achieved by randomizing subjects in a 1:1 ratio to merotocin nasal spray or placebo nasal spray, which are identical in appearance.

At Ferring, personnel at the Bioanalysis Department analyzing blood and milk samples for merotocin will be blinded to treatment allocation when performing the analyses. The rest of the

Ferring clinical trial team will be blinded to individual and group treatment allocation until breaking of the blind after database lock, except for the Safety Committee members who may be unblinded to group treatment allocation under special circumstances (see Section 3.5). DMC members will have access to unblinded interim data to assess the futility at the interim analysis (see Section 3.4).

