Cover page for Protocol

Sponsor name	Ferring Pharmaceuticals Inc.
NCT Number:	NCT02545127
Sponsor trial ID:	000050
Official title of trial:	A randomized, double-blind, placebo-controlled, multicenter trial exploring the efficacy and safety of intra-nasal administration of merotocin in increasing milk production in maternal subjects with preterm delivery and inadequate milk production
Document Date:	06 Apr 2022

CLINICAL TRIAL PROTOCOL

A randomized, double-blind, placebo-controlled, multicenter trial exploring the efficacy and safety of intra-nasal administration of merotocin in increasing milk production in maternal subjects with preterm delivery and inadequate milk production

MERMAID

Merotocin in Mothers with Inadequate Milk Production and Infants Delivered Prematurely

Trial 000050

IND Number: 105928

Investigational Medicinal Product: Merotocin, FE 202767 (Selective oxytocin-receptor agonist, nasal spray)

Indication: Induction and support of lactation in women with preterm delivery and inadequate milk production

Phase: 2

Name and Address of Sponsor: Ferring Pharmaceuticals Inc.
[name]
[name]
United States
Tel: [REDACTED]

GCP Statement: This trial will be performed in compliance with GCP.

The information in this document is confidential and is proprietary to Ferring Pharmaceuticals Inc. or another company within the Ferring Group. It is understood that information in this document shall not be disclosed to any third party, in any form, without prior written consent of an authorized officer of Ferring Pharmaceuticals Inc. or another company within the Ferring Group.

SYNOPSIS

TITLE OF TRIAL

A randomized, double-blind, placebo-controlled, multicenter trial exploring the efficacy and safety of intra-nasal administration of merotocin in increasing milk production in maternal subjects with preterm delivery and inadequate milk production

SIGNATORY INVESTIGATOR

MD, [REDACTED]

TRIAL CENTERS

Approximately 15 trial centers in the United States

PLANNED TRIAL PERIOD

Estimated First Patient First Visit: Q4 2019
Estimated Last Patient Last Visit: Q2 2023

CLINICAL PHASE

2

OBJECTIVES

Primary Objective

- To evaluate the effect of merotocin on increasing milk production in women with preterm delivery and with inadequate milk production

Secondary Objectives

- To evaluate the effect of merotocin on milk production after treatment discontinuation

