5.5 Blinding/Unblinding

5.5.1 Blinding

This trial is a double-blind design in which the investigators and the maternal subjects will be blinded to treatment allocation throughout the trial.

The IMP will be packaged according to a computer-generated randomization list prepared for all trial centers. Merotocin and placebo nasal spray will be indistinguishable with identical appearance. The Ferring Global Biometrics Department will store the randomization list according to Ferring's standard operating procedures. Maternal subject randomization numbers will be linked to IMP numbers via treatment codes. The randomization list will not be available to any person involved in the conduct and evaluation of the trial until the trial database is released to the statistician. All staff at each trial center including the trial medication delegates will be blinded to treatment allocation throughout the trial.

Ferring personnel at the Bioanalysis Department analyzing blood and milk samples for merotocin will be blinded to treatment allocation when performing the analyses. The rest of the Ferring clinical trial team will be blinded to individual and group treatment allocation until after database lock, except for Safety Committee members who may be unblinded to the group treatment allocation under special circumstances. DMC members will have access to unblinded interim data to assess the futility at the interim analysis and will keep the data and analyses confidential.

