7.4 Assessments Related to Post-trial Endpoints

Additional data will be collected from the hospital records of the infant when the infant is discharged from NICU. The additional data (if available) are infant body weight, length and head circumference at time of infant's discharge from NICU, the date when the infant becomes tolerant to full enteral feeding, date of discharge from NICU, number of days the infant requires TPN until discharge from NICU, type of feeding (MoM and formula/donor milk) at time of infant's discharge from NICU, and whether the maternal subject is lactating (i.e., breastfeeding or breast pumping) at time of infant's discharge from NICU.

Concomitant medications and AEs will be collected from hospital records through time of infant's discharge from NICU or until the last milk sample expressed during maternal subject's treatment with IMP is either consumed by the infant or discarded, whichever occurs last. Information on infant's morbidity events of special interest occurring prior to the infant's discharge from NICU, including NEC, intra-ventricular hemorrhage, BPD, RDS, late-onset sepsis, ROP, and hemodynamically significant patent *ductus arteriosus*, are recorded at the time of infant's discharge from NICU based on hospital records. The trial is not powered to draw conclusions on the incidences of these events, but they are collected in order to capture any trends on the impact of feeding patterns on their incidences.

From the follow-up contact about one month after the infant's NICU discharge, the date of any hospital re-admission of the infant occurring since NICU discharge, and the reason for the re-admission will be recorded. Investigators should assess the causal relationship between the reason for such re-admissions and the IMP.

For long-term follow-up, the ASQ-3 will be provided for all infants at 9 months, 18 months and 24 months of corrected gestational age. A primary caregiver of the infant will answer the questionnaire that consists of approximately 30 questions covering five domains of development, including communication, gross motor, fine motor, problem-solving, and personal-social skills. It takes about 15-30 minutes to complete the questionnaire. If a score falls into the black zone of any domain on the scoring summary sheet, standard referral procedures should be followed.

Data from post-trial activities will be provided in an addendum to the clinical trial report.

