8.6.2 Collection of Serious Adverse Events with Onset after Last Trial Visit

If an investigator becomes aware of an SAE of the maternal subject after the Day 18/Follow-up visit, and he/she assesses the SAE to have a reasonable possible causality to the IMP, the case will have to be reported to Ferring, regardless of how long after the end of the trial this takes place.

If an investigator is informed of a hospital re-admission of the infant from the follow-up call about one month after infant' discharge from NICU, and he/she assesses the reason for the re-admission to have a reasonable possible causality to the IMP, the case will be reported as an SAE to Ferring. Similarly, if an investigator becomes aware of an SAE of the infant during the infant's long-term follow-up, and he/she assesses the SAE to have a reasonable possible causality to the IMP, the case will have to be reported to Ferring. The SAE will be followed up until the event is resolved or until the medical condition is stable.

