14.3 End-of-Trial and End-of-Trial Notification

At the end of the trial, i.e., when the last subject completes the Day 18/Follow-up visit, Ferring will notify the appropriate regulatory authority and the IRB about the trial completion in accordance with the local requirements of the country where the trial is conducted.

In case of early termination for safety reasons, Ferring must notify the end of the trial to the national regulatory authority and the IRB in accordance with national/local regulations.

In addition, results of the trial will be provided to the relevant regulatory authority when available and within one year of the trial completion (last maternal subject last visit).

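### The blind is protected only to the main database lock, so later caregiver-answered ASQ-3 questionnaires and causality-dependent late infant SAE reports could be made with knowledge of allocation

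*Combined protocol and SAP*

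**What the plan says.** **End of the blind.** Section 3.6.3 states, for mothers as well as investigators and site staff, that "maternal subjects will remain blinded to treatment allocation until the database has been locked and the trial has been unblinded". Section 5.5.1 says that "the investigators and the maternal subjects will be blinded to treatment allocation throughout the trial", and Section 14.3 places the end of the trial at the point "when the last subject completes the Day 18/Follow-up visit". Section 5.5.1 also lifts the restriction on the randomization list once the database is released to the statistician.

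**Calendar.** The Synopsis gives "Estimated First Patient First Visit: Q4 2019" and a last visit in Q2 2023. Section 3.1.3 lists "Post-trial activities completed" as Q2 2025. Section 14.3 commits to giving the regulator results within one year of the last maternal visit. Post-trial data go into an addendum (Section 7.4) and have their own SAP (Section 9). Section 9 requires the main SAP before the blind is broken but sets no such deadline for the post-trial SAP.

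**What is collected late.** The ASQ-3 is due at 9, 18 and 24 months corrected age. Section 7.4 says: "A primary caregiver of the infant will answer the questionnaire". For an infant SAE that the investigator learns of during long-term follow-up, Section 8.6.2 makes reporting depend on causality: if "he/she assesses the SAE to have a reasonable possible causality to the IMP, the case will have to be reported to Ferring".

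**The concern.** Follow-up outlasts the only stated protection of the blind, and the two kinds of data still arriving are the ones most open to judgement.

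The ASQ-3 is a caregiver report, and a score in the black zone in any domain is a named post-trial endpoint. The caregiver may well be the randomised mother. Someone who knows which spray was used may answer differently, in a direction that cannot be predicted.

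The late-SAE rule asks the investigator for a causality judgement before a report is required. An investigator who knows that the mother received placebo has little basis for calling the event possibly related, so late reports could come mainly from the merotocin arm for that reason alone.

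Beyond the one-month contact, these are the only infant data planned, in the first trial of this drug in its target population. Once allocation is disclosed, the loss cannot be repaired.

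**Working it through.** **1. The plan's own date.** Q2 2023 + 24 months = Q2 2025, which reproduces Section 3.1.3 at quarter level. Because age is corrected, the exact date is birth + (40 - gestational age) weeks + 24 months. An infant born at 34+2 weeks on 1 April 2023 reaches it on 11 May 2025. One born at 24+0 weeks on 15 May 2023 reaches it on 4 September 2025. For the most premature late enrollees, follow-up therefore runs slightly past the stated quarter.

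**2. Main unblinding against end of follow-up.** Results are due by about Q2 2023 + 12 months = Q2 2024. The gap to Q2 2025 is 24 - L months, where L is the lag from last visit to lock: 21, 18 and 12 months for L = 3, 6 and 12. The plan does not state L. The one-year deadline caps it at about 12, and the lower value of 3 is an assumption.

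**3. Share of questionnaires after lock.** Inputs:
- Accrual window A = 42 months (mid Q4 2019 to mid Q2 2023), assumed uniform.
- Prematurity p = 40 weeks minus gestational age. This is 5.7 weeks = 1.3 months at 34+2 and 16 weeks = 3.7 months at 24+0 (range from Section 4.1.1).
- Corrected age c = 24, 18 or 9 months.

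Share = max(0, c + p - L) / A. Each cell runs from p = 1.3 to p = 3.7.

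| c | L = 3 | L = 6 | L = 12 |
|---|---|---|---|
| 24 | 22.3/42 = 53.1% to 24.7/42 = 58.8% | 19.3/42 = 46.0% to 21.7/42 = 51.7% | 13.3/42 = 31.7% to 15.7/42 = 37.4% |
| 18 | 16.3/42 = 38.8% to 18.7/42 = 44.5% | 13.3/42 = 31.7% to 15.7/42 = 37.4% | 7.3/42 = 17.4% to 9.7/42 = 23.1% |
| 9 | 7.3/42 = 17.4% to 9.7/42 = 23.1% | 4.3/42 = 10.2% to 6.7/42 = 16.0% | 0% to 0.7/42 = 1.7% |

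Rounded over L = 3 to 12, this is 32-59%, 17-45% and 0-23%.

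**4. Check by simulation.** The formula counts the lag from the last birth. The last visit can be about 8 + 18 + 2 = 28 days later (0.92 months), which lowers each non-zero share by about 0.92/42 = 2.2 percentage points. A simulation that includes those 28 days, with gestational age uniform over the eligible range and full completion, gives 53.8%, 39.5% and 18.0% at 24, 18 and 9 months for L = 3 (37.1% of all contacts). For L = 12 it gives 32.3%, 18.0% and 0% (16.8% of all contacts).

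**5. Accrual pattern.** The April 2022 amendment widened the gestational-age and randomization windows (Sections 3.6.1 and 3.6.6), so recruitment may be back-loaded. The table shows the share of all ASQ-3 contacts that fall after lock.

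| Accrual | L = 12 | L = 1 |
|---|---|---|
| Uniform | 17% | 42% |
| Half after the amendment | 26% | 55% |
| Three quarters after it | 39% | 73% |

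**6. What is not exposed.**
- Infant AEs to Day 18: 0% after lock, by definition.
- NICU discharge, taken as near term-equivalent age: about 0-4% after lock across these scenarios.
- One-month contact, at 1.3 + 1 = 2.3 to 3.7 + 1 = 4.7 months after birth: for L = 3, 0% to (4.7 - 3)/42 = 4.0%.

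No share can be computed for late infant SAEs, because the documents give no expected rate.

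**The case against.** **The plan does not say that allocations will be disclosed.** Section 3.6.3 sets how long the blind must last. No section says that individual codes go to sites or mothers at unblinding. Section 14.5 offers mothers only the overall findings, the participation card must not reveal allocation (Section 14.6), and the sponsor's biometrics department stores the list. This stands: a reader might infer that the later data will be collected unblinded, but the documents support only that they could be. It does not close the gap. No section withholds allocation after lock, data listings are planned (Sections 9.6.1 and 9.8.2), and an investigator reviews and signs the trial report (Section 13.1).

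**Lock might follow all follow-up.** The documents do not expressly separate a main lock from a final one. But the one-year results deadline, the addendum and the separate post-trial SAP do not fit a single lock in 2025.

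**Most infant safety data are safe.** A reader might infer that much of it is exposed. It is not: infant AEs come from hospital records to Day 18, then to NICU discharge or last use of trial milk, with no causality condition (Section 8.2.4). A reader might also take one-month re-admissions to be filtered by causality. In fact Section 7.4 records the date and reason of any re-admission; only its reporting as an SAE depends on causality (Section 8.6.2).

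**Little rests on the endpoint.** Seven of the eight post-trial endpoints are fixed by NICU discharge, and all are only summarised in tables (Section 9.6.5). Late SAEs are incidental case reports with no planned arm comparison. This stands, and it limits the weight of the point. The documents also contain no evidence that caregivers would score differently by arm.

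**Conclusion.** The concern holds as a gap in protection. The stated blind for investigators, site staff and mothers ends at the main lock and unblinding, about 12 months or more before ASQ-3 follow-up ends. Under uniform accrual and a lock 3 to 12 months after last visit, about 32-59% of 24-month, 17-45% of 18-month and 0-23% of 9-month questionnaires fall in the unprotected period; back-loaded accrual would raise these shares. Late infant SAEs under Section 8.6.2 are exposed in the same way, to an extent that cannot be quantified.

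The lock lag, the accrual pattern and full ASQ-3 completion are assumptions. That main unblinding precedes the end of follow-up is inferred from the reporting arrangements, though firmly.

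A reader might go further and conclude that the post-trial comparison as a whole is biased. The documents do not support that: only the ASQ-3 among the post-trial endpoints is materially exposed. The primary endpoint, the proof-of-concept decision and in-trial safety are untouched. The change is worth making because it is cheap and cannot be made after disclosure.

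**What to change.** Amend Sections 3.6.3 and 5.5.1 to state that:
- at main lock, individual allocation is released only to the sponsor's analysis and reporting team;
- investigators, site staff, mothers and primary caregivers stay blinded to individual allocation, with the existing emergency code-break excepted, until the last 24-month ASQ-3 is entered and the post-trial database is locked;
- until then, any results given to sites or mothers are at group level only.

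In Section 9, require the post-trial SAP to be final before the main unblinding.

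The cost is a few protocol sentences and restricted access to the randomization list. Sites and mothers learn individual allocation later, and subject-level listings are withheld from sites until the post-trial lock.
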